8.2 Method of Detecting and Collecting Adverse Events

Care will be taken to not introduce bias when detecting AEs and/or SAEs. Open-ended and nonleading verbal questioning of the participant is the preferred method to inquire about AE occurrences.

All AEs spontaneously reported by the participant or reported in response to the open question from the study site staff: “Have you had any health problems since the previous visit/you were last asked?” or revealed by observation will be collected and recorded in the eCRF.

8.2.1 Time Period and Frequency for Collecting Adverse Events

All AEs/SAEs will be collected from the time the participant signs the ICF until the completion of the follow-up period (including the extended follow-up). After the follow-up period (including the extended follow-up), any SAE that is related to study treatment by investigator assessment should be reported directly to the Sponsor’s pharmacovigilance team.

8.2.2 Follow-up of Adverse Events

After the initial AE report, the investigator is required to proactively follow each participant at subsequent visits/contacts. All SAEs will be followed until resolution, stabilization, the event is otherwise explained, or the participant is lost to follow-up.

Any AE that is unresolved at the participant's last study visit will be followed by the investigator for as long as medically indicated (this may be beyond the follow-up period), but without further recording in the eCRF. The Sponsor retains the right to request additional information for any participant with any ongoing AEs at the end of the study, if judged necessary.

8.2.3 Adverse Events Based on Laboratory Test and Examination

Safety assessments, including protocol mandatory laboratory tests, ECG, vital signs, and physical examination, as specified in [Section 7.2](#), will be collected and summarized in the clinical study report by worsening shift change from the baseline value. With this objective way of safety analysis, AE reporting based on examinations and laboratory tests by the investigator should well consider the baseline values and dynamic changes over time.

8.2.3.1 Laboratory Abnormality

A laboratory test result (including vital signs, ECG, etc.) must be reported as an AE if it meets any of the following criteria:

- Results in a change in study treatment (e.g., dose modification, treatment interruption or treatment discontinuation)
- Leads to medical intervention (e.g., potassium supplementation for hypokalemia)
- Is clinically significant in the investigator's judgment

It is the investigator's responsibility to review all laboratory findings and to document his/her assessment for abnormal laboratory findings. Medical and scientific judgment should be exercised in deciding whether an isolated laboratory abnormality should be classified as an AE. The AEs relevant to abnormal laboratory values should be followed up till resolution, stabilization (e.g., to baseline value) or an explanation is available, or the participant is lost to follow-up.

Abnormality of a laboratory value, which is unequivocally due to natural disease progression, should not be reported as an AE.

If deterioration in a laboratory value/vital sign is associated with clinical signs and symptoms, the sign or symptom will be reported as an AE, and the associated laboratory result/vital sign will be considered as additional information. Wherever possible the reporting investigator uses the clinical, rather than the laboratory term (e.g., anemia versus low hemoglobin value).

8.2.3.2 Physical examination

Any new or aggravated clinically relevant abnormal medical finding at a physical examination as compared with the baseline assessment will be reported as an AE unless unequivocally related to the disease under study.

8.3 Expedited Safety Reporting

Investigators must fill the SAE report form and other safety report form (e.g., pregnancy report) provided by the Sponsor and report these events to the pharmacovigilance safety database of the Sponsor immediately (within 24 hours of becoming aware of the event), regardless of relationship to the study treatment.

The investigator will submit any updated SAE information to the Sponsor within 24 hours of it being available. For fatal or life-threatening SAEs where important or relevant information is missing, active follow-up is undertaken immediately. Investigators or other site personnel are required to respond to urgent queries immediately but no later than 24 hours of when he or she receives the queries.

Training in SAE reporting will be provided by the Sponsor for each study.

8.4 Pregnancy Report

All pregnancy events must be reported in the period starting from the first dose through completion of the follow-up (including the extended follow-up) period. The pregnancy itself is not considered to be an AE or SAE, while if the pregnancy outcome meets the criteria for an SAE (i.e., ectopic pregnancy, spontaneous abortion, intrauterine fetal demise, neonatal death, or congenital anomaly), the investigator should follow the procedures for reporting SAEs as specified in [Section 8.3](#).

If a female participant becomes pregnant during the study, the investigator must report the pregnancy to the Sponsor within 24 hours of awareness using the Pregnancy Report/Follow-up Form, and to the relevant institutions in a timely manner per local requirement.

The investigator should follow up on the pregnancy outcome (e.g., any early termination of pregnancy, or a live birth) until 4 weeks after delivery and notify the Sponsor and the EC (or other organizations as required by local regulations) of the pregnancy outcome.

If a male participant's partner becomes pregnant during the clinical study, the investigator must report the pregnancy to the Sponsor within 24 hours of learning of the pregnancy and submit the completed Pregnancy Report/Follow-Up Form. Consent should be obtained from the male participant's partner prior to obtaining any pregnancy result and outcome.

Any poststudy pregnancy-related SAE considered reasonably related to the study intervention by the investigator will be reported to the pharmacovigilance team of the Sponsor.

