5.3 Contraception Recommendations

A female who is permanently surgically sterile or postmenopausal is not considered to be a female of childbearing potential and is not required to follow contraception recommendations.

Surgically sterile is defined as:

- Bilateral oophorectomy (surgical removal of both ovaries); or
- Bilateral salpingectomy (surgical removal of both fallopian tubes); or
- Hysterectomy (surgical removal of uterus)

Postmenopausal is defined as no menses for 12 months without an alternative medical cause. A high follicle stimulating hormone level in the postmenopausal range may be used to confirm a postmenopausal state in women not using hormonal contraception or hormonal replacement therapy.

A female who does not meet the definition of postmenopausal or permanently surgically sterile or is postmenarchal or pubertal but has not yet had menses is considered of childbearing potential and is required to practice at least one of the following highly effective methods of birth control consistently from signing of informed consent until 6 months after the last dose of study treatment.

- Combined (containing estrogen and a progestogen) hormonal contraception (oral, intravaginal, transdermal, injectable) associated with the inhibition of ovulation.
- Progestogen-only hormonal contraception (oral, injectable, implantable) associated with inhibition of ovulation.
- Bilateral tubal occlusion/ligation.
- Vasectomized partner(s) provided that the vasectomized partner has received medical confirmation of the surgical success and is the sole sexual partner of the female trial participant of childbearing potential.
- Intrauterine device.
- Intrauterine hormone-releasing system.
- True abstinence (if acceptable per local requirements): Refraining from heterosexual intercourse when this is in line with the preferred and usual lifestyle of the participant. Periodic

abstinence (e.g., using calendar, ovulation, symptothermal, postovulation methods) and withdrawal are not acceptable.

The above-mentioned definition for true abstinence also applies to male participants. Contraception requirements do not apply to participants in an exclusively same-sex relationship.

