11.3.7 Interim Analysis

A first interim analysis (IA) may be performed when all participants have completed the Week 24 (Day 169) visit or discontinued early prior to Week 24 visit. A second IA may be performed when all participants have completed the Week 30 (Day 211) visit or discontinued early prior to Week 30 visit.

Final analysis will be performed when all participants have completed the study (i.e., Week 24 [Day 169]/EOS visit or the Week 36 [Day 253] visit, as applicable) or discontinued early. Details of the IA and the final analysis will be provided in the SAP.

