## 5.5 Participant Disposition

Summaries will be provided for the following data in each treatment group for the full study sample (i.e., all screened participants who signed informed consent):

- The number and percentage of participants screened, and who failed screening, along with the reasons for screen failure. (This will be reported only in the overall group.)
- The number and percentage of participants included in each treatment group as well as in each study analysis set.
- The number and percentage of participants who completed the 4-week dosing period, discontinued the 4-week dosing period with the reason for discontinuation, completed the 16-week treatment period, discontinued 16-week treatment period with reason for discontinuation, completed the study, and discontinued the study with reason for discontinuation, consented for the extended follow-up, completed the extended follow-up, and discontinued the extended follow-up with reason for discontinuation.

A summary will be provided for major protocol deviations by deviation category and treatment group for the safety analysis set. The protocol deviations flagged as ‘CSR Reportable’ will be classified as major protocol deviations.

The following listings will be provided.

- The participant disposition listing comprises various details, including the date of informed consent form (ICF) signing, ICF and protocol versions, enrolment or screen failure dates, and the completion/discontinuation date of the 4-week dosing period, date of 16-week treatment period/discontinuation, reason for discontinuation, study completion status, date of study completion, among other factors.
- A listing of screen failures with inclusion criteria not met and/or exclusion criteria met.
- Listing of protocol deviation.

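### Protocol 8.4 does not tie pregnancy reporting to the 6-month post-dose contraception period, so a pregnancy after exit at Week 24 or earlier may go unreported

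*Protocol*

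**What the plan says.** Reporting window. Protocol 8.4: "All pregnancy events must be reported in the period starting from the first dose through completion of the follow-up (including the extended follow-up) period". The duty for women reads: "If a female participant becomes pregnant during the study, the investigator must report the pregnancy to the Sponsor within 24 hours of awareness". The duty for partners of male participants is likewise limited to pregnancies arising while the clinical study runs. Reported pregnancies are followed to 4 weeks after delivery.

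After the study. Protocol 8.4: "Any poststudy pregnancy-related SAE considered reasonably related to the study intervention by the investigator will be reported to the pharmacovigilance team of the Sponsor".

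Contraception period. Protocol 5.3 requires women of childbearing potential to use a highly effective method "consistently from signing of informed consent until 6 months after the last dose of study treatment". Protocol 5.1 gives the same end for women and a minimum of 6 months for men, and bars egg and sperm donation over that time. Protocol 7.2.5 instead speaks of contraception for the duration of the study.

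Who may leave before Week 36. Protocol 4.1.2 plans extended follow-up to Day 253 for each cohort. Protocol 11.3.7 nevertheless describes study completion as the "Week 24 [Day 169]/EOS visit or the Week 36 [Day 253] visit, as applicable", and SAP 5.5 counts separately those who "consented for the extended follow-up, completed the extended follow-up". Protocol 6.10.2 allows withdrawal at any time. Protocol 6.10.1.1 asks those who stop treatment early for their remaining visits only as far as end of study, which is Week 24.

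**The concern.** The two rules run on different clocks. Contraception is counted from the last dose; pregnancy reporting is counted by study follow-up. They agree for anyone who stays to Week 36. For anyone who leaves sooner, there can be a stretch in which the protocol still requires contraception but does not clearly require a new pregnancy to be reported.

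The sentence on events after the study narrows the gap but does not close it. It reaches only a pregnancy-related serious adverse event that the investigator judges related. An ongoing normal pregnancy, or a loss judged unrelated, would not trigger a report, and the follow-up to 4 weeks after delivery would not start. Protocol 6.6 says that clinical experience with IMG-007 is limited, so the outcome of each exposed pregnancy is informative and may be hard to recover later.

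**Working it through.** Inputs:
- Planned last dose on Day 29 (Protocol 6.4). A 10-day delay of that dose is allowed (6.5), so Day 39 at the latest.
- End of treatment on Day 113, end of study on Day 169, Week 30 on Day 211, Week 36 on Day 253 (4.1.2).
- Contraception for 6 months after the last dose (5.1, 5.3). The documents do not give this in days. I assume 181 to 184 calendar days, and 168 days (24 weeks) as the shortest reading.

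Step 1, the plan's own figures. Protocol Table 5 places the end-of-study sample 140 days after the third dose: 169 − 29 = 140. The Day 113 and Day 141 entries also agree: 113 − 29 = 84 and 141 − 29 = 112.

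Step 2, end of the 6-month period = last-dose day + 181 to 184. Gap = that day − exit day.

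| Last dose | 6 months ends | Gap, exit Day 169 | Gap, exit Day 113 |
|---|---|---|---|
| Day 29 (three doses) | Day 210–213 | 41–44 days | 97–100 days |
| Day 39 (third dose delayed) | Day 220–223 | 51–54 days | 107–110 days |
| Day 15 (two doses) | Day 196–199 | 27–30 days | 83–86 days |
| Day 1 (one dose) | Day 182–185 | 13–16 days | 69–72 days |

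On the 168-day reading, a Day 29 last dose gives Day 197, and the gap at Day 169 is 197 − 169 = 28 days.

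Step 3, full follow-up. 253 − 29 = 224 days, which passes the 6-month point by 253 − 213 = 40 to 253 − 210 = 43 days. With the last dose on Day 39, 253 − 39 = 214 days, and the margin is 30 to 33 days. No gap remains in either case. Leaving after Week 30 gives at most 213 − 211 = 2 days, or 9 to 12 days if the last dose was on Day 39.

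Step 4, detection. The pregnancy-test windows in SAP 11.3 (Group 4) include Week 24 and Week 36 but not Week 30. For anyone who does not reach Week 36, Day 169 is therefore the last scheduled test at best. Neither document plans a contact after exit.

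**The case against.** The planned course has no gap. Every cohort is scheduled to Day 253, 8.4 names the extended follow-up explicitly, and the schedule includes a serum test there.

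The wording of 8.4 can also be read more generously. The extended follow-up is defined by calendar days (Day 169 to 253), so its completion might mean Week 36 for everybody. Protocol 4.2 ends the study only when the last participant finishes, so a person who left at Week 24 might still count as pregnant during the study. Protocol 8.3 asks for pregnancy reports within 24 hours whatever the relationship to treatment, and gives no end date. These readings stand as possibilities: they make the text ambiguous, not plainly wrong. They do not settle it, because no sentence links reporting to 6 months after the last dose and nothing after exit would bring a pregnancy to the site's notice.

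Three stronger readings are tempting and should not be adopted:
- A reader might call the 6 months the protocol's exposure risk period. The protocol sets it only as a contraception and gamete-donation period.
- A reader might infer that pregnancies in early leavers go unreported altogether. Those that occur before exit are reportable and followed up.
- A reader might infer that the plan expects participants to finish at Week 24. Protocol 11.3.7 and SAP 5.5 allow it, but neither says how many. Protocol 2.5.1 says that the extension was added, so both phrases may concern people already enrolled at that time. That is an inference.

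Large gaps can be constructed. Exit at Day 43 after three doses leaves about 169 days (29 + 183 − 43). That is a worst case, not a typical figure.

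**Conclusion.** The point holds as a limited gap in safety reporting. It concerns pregnancies after exit, in participants or partners, where the participant leaves before the 6-month point. For exit at Week 24 the uncovered time is 41 to 44 days after a Day 29 last dose, or 51 to 54 days after a Day 39 last dose, and less after one or two doses. For exit at Day 113 after three doses it is 97 to 100 days. Participants who complete Week 36 have none.

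This rests on two assumptions: that 6 months means 181 to 184 days, and that follow-up in 8.4 ends with the participant's own last visit. On a fixed Week 36 reading the reporting gap disappears on paper, and only the lack of a contact after exit remains.

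Severity is minor. Few of about 30 participants are likely to be affected, the documents give no number for them, and no endpoint or efficacy analysis changes.

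**What to change.** In Protocol 8.4, state that pregnancies in participants and in partners of male participants are reportable until the later of the participant's last study visit and the end of the 6-month post-dose period already set in 5.1 and 5.3, whether or not the participant enters the extended follow-up. Refer to that period rather than restating it, so that the two cannot drift apart. Reconcile 7.2.5 with 5.1 and 5.3 in the same edit, because they give different ends for contraception.

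Add one telephone contact at that date for women of childbearing potential and for male participants who left before it and still consent to contact.

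The cost is a few sentences and a few calls, some of which will go unanswered. Participants who withdrew consent or were lost to follow-up will still be missed, and they include some of those with the longest gaps.

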9 SAFETY MONITORING

9.1 Safety Review Committee

A SRC consisting of three independent physicians will convene to review safety data, dose escalation criteria, and the study stopping criteria. The CRO and Sponsor medical monitors will confirm and document in the study file the dose escalation decision before dosing in the subsequent cohort can proceed. The SRC membership, roles and responsibilities, meeting schedules, communication plans, and other details will be documented in the SRC Charter.

Recommendations by the SRC will be shared with the investigators.

10 DATA MANAGEMENT

The investigators are responsible for the accuracy, compliance to the protocol, completeness, and legibility of data documented in the eCRF and in the source documents. All data will be entered by the investigators or authorized trial team members at the site using a validated remote electronic data capture (EDC) system. The EDC system complies with all relevant regulations of the US FDA, with Part 11 of Title 21 of the Code of Federal Regulations (21 CFR Part 11: Electronic records; Electronic signatures), and other local regulations, if applicable. Discrepancy in the data will be brought to the attention of the clinical team and the investigational site personnel, if necessary. Resolution of these issues will be reflected in the database. Data management details will be outlined in a separate data management plan.

All aspects of the study will be carefully monitored by the Sponsor or its authorized representatives for compliance and applicable regulations with respect to the current GCP and standard operating procedures.

The Sponsor ensures that appropriate monitoring procedures are performed throughout the study. During monitoring visits, the facilities, investigational product storage area, CRFs, participant's source documents, and all other study documentation will be inspected/reviewed by the Sponsor representative in accordance with the Study Monitoring Plan. Accuracy will be checked by performing source data verification or source data review, comparing entries made into the CRFs against appropriate source documentation. Any resulting discrepancies will be reviewed with the investigator and/or his/her staff. Any necessary corrections will be made directly to the CRFs or via queries.

Monitoring details describing strategy, including definition of study critical data items and processes (e.g., risk-based initiatives in operations and quality, such as risk management and mitigation strategies and analytical risk-based monitoring), methods, responsibilities, and requirements, including handling of noncompliance issues and monitoring techniques (central, remote, or on-site monitoring) will be documented in the Study Monitoring Plan.

11 STATISTICAL CONSIDERATIONS

11.1 Sample Size Determination

11.2 Analysis Sets

- Safety analysis set will be used for safety analyses, which will include all participants who received at least one dose of study treatment. Participants will be analyzed by the dose received. Safety analysis set will also be used for demographic and baseline characteristics.
- Modified full analysis set will be used for efficacy analyses, which will include all participants who received at least one dose of study treatment.
- PK analysis set will be used for PK and ADA analyses, which will include all participants in the safety analysis set who also have baseline and at least one post-baseline evaluable data point.
- PD analysis set will be used for PD analyses, which will include all participants in the safety analysis set who also have baseline and at least one post-baseline evaluable PD/biomarker data point.

11.3 Statistical Analysis

11.3.1 Analysis of Safety

Safety variables including incidence, severity, and changes from baseline of relevant parameters (such as vital signs, ECGs, and clinical laboratory values) will be summarized.

- AEs will be coded using the Medical Dictionary for Regulatory Activities (MedDRA, the version currently in use by the Sponsor at the time of database lock). TEAEs are defined as events started after the initiation of the first dose of study treatment or events present that worsen after the start of dosing. The number and proportion of participants experiencing one or more TEAEs will be summarized by severity, and relationship to study treatment.
- Prior and concomitant medications will be coded using the World Health Organization Drug Dictionary. The number and proportion of participants taking prior and/or concomitant medications will be summarized.
- Vital signs (systolic and diastolic blood pressure, pulse, respiratory rate, and temperature) and ECG parameters will be summarized by visit descriptively. Changes from baseline, number, and proportion of participants with clinically important values will be presented descriptively.
- Clinical laboratory parameters, including changes from baseline, where appropriate, will be summarized using descriptive statistics, by post-dosing shift from baseline in the normal or abnormal category of laboratory values by visit, and number and proportion of participants with a treatment-emergent clinically significant abnormal value based on predefined criteria, and data listings.

